3.3 Vulnerable Subjects

No vulnerable populations will be enrolled in this study.

3.4 Recruitment and Consent

Surgeon will identify potential subjects during their initial preoperative visit at which the surgeon will discuss the study with the patient. Should the potential subjects agree, the surgeon will provide the researcher with the name and medical record number of the patient. Researchers will receive the name and MRN of potential subjects identified by treating physician (study team members not volunteers) will utilize EPIC to extract patient demographic and surgical information to determine study eligibility. Once eligibility is confirmed, the treating physicians (TPs) will be notified via email, and they will discuss the study with the patient in the clinic at least 1 day prior to surgery to allow potential subjects to review and consider participation in the study.

If a subject requests information regarding opting out of further recruitment for all research, subjects will be directed to contact study coordinator or have subjects contact [contact] or [name].

CONFIDENTIAL

This material is the property of the NYU School of Medicine and Langone Medical Center. Do not disclose or use except as authorized in writing by the study sponsor

Written consent will then be obtained on the day of surgery in the preoperative holding area by an authorized research team member or the treating physician (surgeon or anesthesiologist). Once the patient is enrolled, they will be assigned a subject ID number and be randomized into a treatment group.

Once enrolled in the study, subject medical records will be accessed once more after surgery (for the second and final time) using subject MRNs by authorized study team members to collect demographic data including age, BMI, sex, smoking history, past surgical history, intraoperative findings, and opioid consumption (mgs) in the PACU. Once collected, deidentified data will be stored in the MCIT-managed HIPAA-compliant and encrypted version of Redcap in addition to the MCIT governed, firewall protected shared drive located on the NYU MCIT network.

Data linking protected health information to the deidentified patient record number will be kept in a local password-protected computer. Only the principal investigator will have access to the identified data.

Process of Consent

Written consent for participation will be obtained on day of surgery in pre-operative holding room by the Attending Physicians, or authorized researchers that are members of the study team. Extensive discussion of risks and possible benefits of participation will be provided to the participants and their families. Consent forms will be IRB-approved, and participants will be asked to read and review the document. The investigator will explain the research study to the participant and answer any questions that may arise. All participants will receive a verbal explanation suited to their comprehension of the purposes, procedures and potential risks as well as their rights as research participants. Participants will have the opportunity to carefully review the written consent form and ask questions prior to signing. The participants will have the opportunity to discuss the study with their surrogates or think about it prior to agreeing to participate. The participant will sign the informed consent document prior to any procedures being done specifically for the study. The participants may withdraw consent at any time throughout the course of the trial. A copy of the key information form document will be given to the participants for their records. The rights and welfare of the participants will be protected by emphasizing that the quality of their medical care will not be adversely affected if they decline to participate in this study. If possible, subjects will be given a copy of the informed consent form at their pre-surgical visit to allow them time to read through it, discuss with their relatives, and contact the study team with any questions prior to their surgery.

A copy of the signed informed consent document will be given to the patient, placed in the patient's electronic medical record and the original copy will be stored in the research regulatory binder. Any alteration to the standard consent process (e.g., use of a translator, consent document presented orally, etc.) and the justification for such alteration will likewise be documented.

Capacity will be assessed through the subject's ability to express understanding of the information being presented to them. The subject will be asked to state back the goals of the study and that they are willing to participate in their primary language.

3.5 Duration of Study Participation

The study will remain open until 50 patients are recruited for each intervention arm of the study. The actual subject participation length will be seven days.

3.6 Total Number of Participants and Sites

Recruitment will end when 100 participants have been enrolled. It is expected that there will be subjects enrolled who will be lost to follow up and be evaluated by intention-to-treat. The sites for enrollment will be the NYU Langone Orthopedic Hospital and NYU Ambulatory Surgery Center at 38th street.

CONFIDENTIAL

This material is the property of the NYU School of Medicine and Langone Medical Center. Do not disclose or use except as authorized in writing by the study sponsor

3.7 Participant Withdrawal or Termination

Participants are free to withdraw from participation in the study at any time upon request. An investigator may terminate participation in the study if:

- Any clinical adverse event (AE), laboratory abnormality, or other medical condition or situation occurs such that continued participation in the study would not be in the best interest of the participant
- The participant meets an exclusion criterion (either newly developed or not previously recognized) that precludes further study participation

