Endpoint	Primary Endpoint: Opioid utilization for the first 72 hours after surgery, including during surgery, calculated as morphine equivalent. Secondary Endpoints: Opioid consumption Post-operatively Patient reported VAS scores in PACU Length of stay in PACU Patient reported VAS scores on POD 1, POD 2, POD 3, POD 7 Reaction to IPACK block Incidence of postoperative complications
Study Duration	The study will continue until 50 subjects are enrolled per arm, to allow for potential dropout and increased power.
Participant Duration	Each participant will be enrolled on DOS and complete their final follow up on postoperative day seven.
Duration of IP administration	Once during surgery
Population	50 patients per study arm scheduled for ACLR with BPTB autograft
Study Sites	NYU Langone Orthopedic Hospital and NYU Ambulatory Surgery Center at 38 th street
Number of participants	100
Description of Study Agent/Procedure	Patients in both the study and control group will receive the standard of care adductor canal block composed of 15 mL of Bupivacaine (0.25%). Patients in the study group will receive the additional IPACK block performed using 20 mL of Bupivacaine (0.25%) injected into the interspace between the popliteal artery and capsule of the knee. Patients will be blinded to their group allocation.
Reference Therapy	Reference is isolated adductor canal block
Key Procedures	Adductor canal block 15 mL 0.25% Bupivacaine, IPACK block with 20 mL 0.25% bupivacaine

CONFIDENTIAL

This material is the property of the NYU School of Medicine and Langone Medical Center. Do not disclose or use except as authorized in writing by the study sponsor

Statistical Analysis	Continuous and categorical baseline characteristics will be compared using Hedges standardized difference. Normally distributed data will be compared using t tests while non-normally distributed continuous outcomes will be assessed using the Mann-Whitney U test.
----------------------	--

CONFIDENTIAL

This material is the property of the NYU School of Medicine and Langone Medical Center. Do not disclose or use except as authorized in writing by the study sponsor

1 Background and Specific Aims

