3.2 Exclusion Criteria

- Patients younger than 18 and older than 75.
- Patients with multi-ligament injury
- Patients undergoing concomitant cartilage procedure or osteotomy.
- Patients with a history of chronic pain that have used opioids for pain management for 3 months or longer.
- Patients who are allergic to oxycodone;
- Patients with diagnosed or self-reported cognitive dysfunction;
- Patients with a history of neurologic disorder that can interfere with pain sensation;
- Patients with a history of drug or recorded alcohol abuse;
- Patients who are unable to understand or follow instructions;
- Patients with severe liver disease, renal insufficiency, congestive heart failure, and/or significant heart disease;
- Patients with an allergy or contraindication to any of the medications used in the study, or patients with a contraindication to any study procedures;
- Patients with a BMI over 45;
- Any patient that the investigators feel cannot comply with all study related procedures;
- Any pregnant patient; assessed via urine pregnancy test in the preoperative area as part of standard preoperative surgical protocol;

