4.2.5 Withdrawal/Early Termination Visit

Subjects may discontinue their participation in the study at any time. As there is only a single intervention, and the safety of this is not in question, further follow up will not be required if a subject decides to terminate their participation in the study.

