6.1 General Approach

The primary analysis will follow the intention-to-treat (ITT) principle in order to evaluate the true outcome of the intervention as experienced by the patient who is blinded to the intervention.

Continuous and categorical baseline characteristics will be compared using Hedges standardized difference. Normally distributed data will be compared using t tests while non-normally distributed continuous outcomes will be assessed using the Mann-Whitney U test.

It is anticipated that the data for some subjects will be incomplete for various reasons: missing diary entries, refusal to answer a question on the questionnaire, onset of illness, loss-to-follow-up, etc. All occurrences of incomplete data will be investigated to carefully document the reasons for the missing data. If the primary outcome (amount of opioid utilization for the first 24 hours after surgery) cannot be ascertained with a reasonable degree of certainty, the patient will be excluded from the study.

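### Section 3.7 lets an investigator end a randomised patient's participation after the single block, and nothing keeps that patient in outcome collection or in the intention-to-treat analysis

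*Combined protocol and SAP*

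**What the plan says.** Section 3.7 gives an investigator two grounds for ending participation. The first is an adverse event, laboratory abnormality or other situation that "occurs such that continued participation in the study would not be in the best interest of the participant". The second is that "The participant meets an exclusion criterion (either newly developed or not previously recognized) that precludes further study participation". Neither ground is tied to a time relative to randomisation or to the block.

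Two of the exclusion criteria in section 3.2 could first be met or noticed after randomisation: "Patients undergoing concomitant cartilage procedure or osteotomy" and "Any patient that the investigators feel cannot comply with all study related procedures".

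The Protocol Summary gives the duration of administration as "Once during surgery". Section 3.5 says "The actual subject participation length will be seven days". After the block, participation consists of PACU assessments, contacts on POD 1, 2 and 3, and the POD 7 visit.

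On analysis, section 6.1 states "The primary analysis will follow the intention-to-treat (ITT) principle", and section 3.6 says that patients lost to follow-up will be evaluated by intention-to-treat. Section 6.1 also says that a patient whose primary outcome cannot be established with reasonable certainty is excluded from the study.

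On follow-up after early termination, section 4.2.5 says "As there is only a single intervention, and the safety of this is not in question, further follow up will not be required". The rest of that sentence confines it to a subject who chooses to stop.

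**The concern.** Section 3.7 reads like a rule for a trial with continuing treatment, where ending participation stops exposure. Here, once the block is in, ending participation stops only measurement. The decision is discretionary and comes after randomisation. It can rest on events related to the outcome, such as a harder recovery, a larger operation than planned or poor compliance with contacts.

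If contact ends before the primary outcome is complete, section 6.1 removes the patient from the comparison. Balance created by randomisation is then no longer assured. Removing high opioid users from the IPACK arm would flatter the block, and removing them from the control arm would hide a benefit. Repairing the missing-outcome sentence in 6.1 alone would not recover data that were never collected because participation had been ended under 3.7.

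**Working it through.** **The route, step by step**

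1. Allocation precedes surgery (sections 2.1, 4.2.2 and 6.4), and the block is given once. There is a short interval between opening the envelope and the block, and then seven days of observation. Section 3.7 covers both.
2. The cartilage criterion could be met at operation, although the protocol does not say when such procedures are decided. The compliance criterion rests on what investigators feel, so a missed call could prompt it.
3. No section says whether outcome data are still collected after an investigator ends participation. Section 4.2.5 addresses only termination by the subject.
4. Without POD contacts the primary outcome may be missing, and 6.1 then excludes the patient. How long contact must last is itself unclear: the window is 72 hours in the Protocol Summary and section 1.3, but 24 hours in 6.1 and 6.2. Under 24 hours, a patient terminated after the POD 1 contact may already have the primary outcome. Under 72 hours, contacts to POD 3 are needed.
5. Only patients are said to be blinded. Section 6.4 gives the envelope to the anesthesiologist, and section 5.1 has the surgeon taking part in aspiration before injection. No masking is stated for whoever decides on termination.

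**The plan's own figure**

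Section 6.3 gives 42 per group for a two-sided two-sample t test, alpha 0.05, power 0.80 and an effect called moderate, with no number attached. The 42 cannot be reproduced from those inputs. At an assumed d = 0.5 the t test needs 64 per group. Solving backwards, 42 per group corresponds to d = 0.619. Enrolling 50 per arm allows for the loss of 8 (1 − 42/50 = 16%). That margin protects power against losses but does not protect against selective loss.

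**Illustrative size (assumptions, not figures from the documents)**

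If a fraction f of one arm is removed and those patients average s SD above the arm mean, the arm mean falls by f·s/(1 − f).

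- f = 3/50 = 0.06, s = 1: 0.06/0.94 = 0.064 SD, which is 10% of 0.619.
- f = 5/50 = 0.10, s = 1.5: 0.15/0.90 = 0.167 SD, which is 27% of 0.619.

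A simulation (20,000 runs, normal outcome, no true effect, 50 per arm, removals from one arm only) gives:

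| Removed from one arm | Random from upper half: bias (SD) | Type I error | Highest users: bias (SD) | Type I error |
|---|---|---|---|---|
| 1 | 0.02 | 0.048 | 0.05 | 0.064 |
| 3 | 0.05 | 0.053 | 0.12 | 0.103 |
| 5 | 0.09 | 0.068 | 0.19 | 0.175 |
| 8 | 0.15 | 0.104 | 0.28 | 0.318 |

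The formula agrees with the milder column. The upper half of a normal distribution averages 0.798 SD above the mean, so f = 0.06 gives 0.06 × 0.798/0.94 = 0.051, and f = 0.10 gives 0.10 × 0.798/0.90 = 0.089.

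**Safety**

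Section 7.4 follows adverse events to resolution. It records events for 7 days (non-serious) or 30 days (serious) after the last day of participation, and it provides for events after a subject has discontinued. Two things are lost: the inquiry made at each scheduled visit, and part of the recording window. A patient terminated on POD 1 instead of POD 7 has a window that closes 7 − 1 = 6 days earlier.

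**The case against.** The strongest reply is that section 3.7 is narrower than it looks. An adverse event counts only if it passes a best-interest test, and an exclusion criterion only if it precludes participation. A phone call or a routine POD 7 visit would seldom meet either. That stands as far as frequency goes, and a reader who infers that any adverse event or any late-found criterion permits termination goes beyond the text. But the first test is left undefined and the second is close to circular, so neither gives a firm limit once only observation remains.

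Second, a reader might infer that unmasked investigators make these decisions. The documents do not show that. They show the anesthesiologist receiving the allocation and the surgeon present at the injection, and they say nothing about who decides. Knowledge of the arm is a possibility. Without it, an added procedure for a lesion that predates randomisation would be balanced in expectation.

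Third, section 3.7 says nothing about analysis sets, so it does not itself exclude anyone. That is correct: the loss arises from 3.7 together with the exclusion sentence in 6.1 and the silence on continued collection.

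Fourth, section 4.2.5 might be taken to waive follow-up for everyone who stops. It applies only when the subject chooses to stop, so it leaves termination by an investigator unaddressed.

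Fifth, a reader might infer that patients leave safety follow-up, contradicting 7.4. Section 7.4 continues after discontinuation, so there is no direct contradiction.

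Finally, ending participation between allocation and the block can still prevent study treatment. It would therefore be wrong to say that termination after randomisation never protects a patient, or to bar it from randomisation onward.

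**Conclusion.** The point holds as a gap between sections. A discretionary decision after randomisation can end outcome collection, and 6.1 can then take the patient out of an analysis described as intention-to-treat. Selective removal is a risk and has not been shown to occur.

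Its size cannot be derived from the documents. For 3 to 5 of 50 high users removed from one arm only, the bias is about 0.05 to 0.19 SD, with type I error from 0.053 to 0.175 against a nominal 0.05. At the mild end that is minor, and balanced removal would leave little bias. The range rests on the assumed counts, a normal outcome and one-sided removal. The percentages of the design effect also rest on the back-solved d = 0.619.

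The safety consequence is limited to lost scheduled inquiries and an earlier recording cut-off. This is a cheap improvement, worth making because the patients can still be contacted at no extra visit.

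**What to change.** In section 3.7, separate the end of study procedures from the end of data collection:

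- When an investigator ends study procedures for a randomised patient, including for a newly recognised exclusion criterion or a concomitant procedure, record the reason as an adverse event or protocol deviation, as applicable.
- Keep that patient in the scheduled POD 1–3 and POD 7 data collection and in the intention-to-treat set, unless the patient withdraws consent for follow-up.
- Leave decisions about giving or withholding the block, and all clinical care, with the treating clinicians at any time.
- Reconcile 3.6, 3.7, 4.2.5 and 6.1, so that one rule states who is followed and who is analysed.

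The cost is protocol wording, since the contacts are already scheduled. The small downside is that a few ineligible patients remain in the intention-to-treat set and may slightly dilute the effect.

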3.8 Premature Termination or Suspension of Study

This study may be temporarily suspended or prematurely terminated if there is sufficient reasonable cause. If the study is prematurely terminated or suspended, the PI will promptly inform the IRB and will provide the reason(s) for the termination or suspension.

Circumstances that may warrant termination or suspension include, but are not limited to:

- Determination of unexpected, significant, or unacceptable risk to participants;
- Demonstration of efficacy that would warrant stopping;
- Insufficient compliance to protocol requirements;
- Data that are not sufficiently complete and/or evaluable; or
- Determination of futility

4 Study Procedures and Schedule

4.1 Study Procedures/Evaluations

4.1.1 Study Specific Procedures

Patients will be screened for eligibility by the surgical team during their pre-surgical office visit. Surgeons will explain the study to the eligible patient.

If patients are agreeable to participation, a research team member will provide further details and ask for participation on day of surgery. Informed consent will be obtained on day of surgery when the patient is in the pre-operative holding room by an authorized research member. Patient will complete a **baseline pain assessment as part of the research study**.

Patients in both the study and control group will receive the standard of care adductor canal block composed of 15 mL of bupivacaine (0.25%). Patients in the study group will receive the additional IPACK block performed using 20 mL of bupivacaine (0.25%) injected into the interspace between the popliteal artery and capsule of the knee. This use of bupivacaine (0.25%) in this dosage is consistent with its approved use for peripheral nerve blocks of the lower extremity, per the package insert.

Postoperatively, pain will be assessed via visual analog scale (VAS) by nursing staff during the post-operative period as per standard of care. The VAS pain scores are collected and documented in the patient's electronic medical record. Additionally, while the patient is in the PACU, an authorized research member will visit the patient and administer a pain questionnaire (VAS and McGill Pain scale). Data on PACU opioid use documented in EPIC will be collected.

4.1.2 Standard of Care Study Procedures

The subjects receiving standard of care procedures will undergo adductor canal block with 15 mL of 0.25% bupivacaine. Although not standard of care at this institution, the addition of IPACK block is widely accepted as a standard part of multimodal analgesia in ACLR.

CONFIDENTIAL

This material is the property of the NYU School of Medicine and Langone Medical Center. Do not disclose or use except as authorized in writing by the study sponsor

4.2 Study Schedule

4.2.1 Screening

Screening Visit (Pre-surgical office visit -30 to -1 days)

- Review medical history to determine eligibility based on inclusion/exclusion criteria.
- Review medications history to determine eligibility based on inclusion/exclusion criteria.
- Provide participants with further details regarding their participation on day of surgery and follow up.

4.2.2 Enrollment/Baseline

Enrollment/Day of surgery (Visit 1, Day 0)

- Obtain informed consent of potential participant verified by signature on study informed consent form.
- Verify inclusion/exclusion criteria.
- Complete baseline global health and pain assessment
- Randomize to ACB or ACB + IPACK group
- Perform surgery with analgesic intervention determined by randomization
- Record vital signs, opioid usage, results of examinations, other pain assessments.
- Continue observation in PACU preceding discharge, including administration of VAS scores, pain questionnaire, and opioid usage monitoring.

